4.1 Study design and randomisation

This study will adopt an open labelled wait list RCT design (**Figure 1**). Participants will be randomly assigned using a computer-generated sequence into either the (i) low-intensity online intervention (LiON) group (n = 60) or (ii) wait list control (WLC) group (n = 60) in a 1:1 ratio. This study design was adopted to ensure all participants will be able to receive LiON during the period of this study.

Those randomised to the LiON intervention group will first receive the 4-week LiON, with generic self-help tips provided to each participant before completing the T2 assessment. Meanwhile, those randomised to the WLC group will first receive generic self-help tips for a period of 4 weeks, followed by the 4-week LiON before completing the T2 assessment.

Random blocks will be used for randomisation.

^aDuring the review session, the trained interventionist will discuss the concerns and needs of the potential participant to determine the goal of the 4-week LiON sessions, ensure the potential participant meets the inclusion and exclusion criteria of the study, and provide initial briefing about the LiON (including module structure, components of focus).

Figure 1. Flow of the study recruitment and assessment process.

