The findings of our pilot study (n = 34) suggested that LiON yields an effect size of 0.4 when compared with controls with no intervention at all. To test the main hypothesis that LiON is more effective in reducing participant's distress level than online self-help tips, we estimate the effect size could be halved, with alpha = 0.05 and power = 80%, 52 subjects are needed for each group totalling 104 subjects. After accounting for a 15% attrition, we target 120 subjects for the current study.

7. Statistical Analysis

All statistical analyses will be carried out using IBM® SPSS® with the significance level set at 0.05. Repeated measure ancova model will be used to compare the changes of distress level between two groups with adjustment for the variables that exhibit baseline differences.

A planned analysis will take place after data is available for the first 60 subjects, to provide a more accurate estimate of the power of the study to adjust the final sample size and allocation to the study arms, according to the principles of adaptive trial design.

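### In its usual SPSS form the repeated-measures ANCOVA of section 7 drops anyone with a missing visit unless missing data are handled separately; a mixed model would keep the observed scores

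*Protocol*

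**What the plan says.** Section 7 of the Protocol gives one model for the comparison of the arms: "Repeated measure ancova model will be used to compare the changes of distress level between two groups", with covariates chosen from variables that differ at baseline. On software and error level it adds "All statistical analyses will be carried out using IBM® SPSS® with the significance level set at 0.05". It does not say which SPSS procedure is meant, which visits enter the model, who is analysed, or what happens when a visit is missing.

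Section 3.2 has three assessments: T0 before the intervention, T1 after it, and T2 one month later. Section 3.2.1 places the primary outcomes at both T1 and T2. Section 4.1 states "This study will adopt an open labelled wait list RCT design". It allocates 60 participants to each arm and has the wait-list arm receive its own four weeks of LiON before T2.

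Section 6 gives the sizing: "alpha = 0.05 and power = 80%, 52 subjects are needed for each group totalling 104 subjects". It then adds: "After accounting for a 15% attrition, we target 120 subjects for the current study".

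**The concern.** The method most people mean by repeated-measures ANCOVA in SPSS is the GLM repeated-measures procedure. It holds each participant as one row and needs a value at every visit in the model. A row with a gap is deleted whole, so someone with T0 and T1 but no T2 also disappears from the T1 comparison.

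That is a poor exchange in this design. T1 is the only visit at which one arm has had LiON and the other has not. By T2 both arms have had it. Listwise deletion would therefore discard good data on the contrast of interest because of a gap at a visit that no longer contrasts LiON with no LiON.

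Two things are at stake. One is precision, since observed scores are thrown away. The other is the randomised comparison: if those who leave differ between arms in how distressed they are, the remaining groups are no longer comparable. The trial is open-label. Between T1 and T2 one arm has only self-help tips left while the other is receiving the sessions it waited for, so different reasons for leaving are conceivable.

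**Working it through.** **1. The plan's attrition step.** Inputs from section 6: 104 participants needed, 15% attrition, target 120.

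- Multiplying up: 104 × (1 + 0.15) = 119.6, rounded to 120. This is the stated target.
- Dividing by the retained fraction: 104 / (1 − 0.15) = 122.4, rounded up to 123.

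The two differ by 3, which is small.

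**2. What complete-case handling would leave.** 120 × 0.85 = 102 kept and 120 × 0.15 = 18 dropped, or 51 per arm if losses are equal. That is 104 − 102 = 2 below the plan's own number.

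**3. How many of the 18 have a usable T1 score.** The Protocol does not split attrition by visit, so this is a range.

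- If everyone lost leaves before T1, a mixed model rescues none.
- If everyone lost leaves between T1 and T2, it rescues all 18 T1 scores.
- For an assumed middle case (10% missing T1, 15% missing T2, nobody returning after a gap): 120 × (0.15 − 0.10) = 6 T1 scores.

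**4. Bias on the T1 contrast in that middle case.** Assume that the LiON participants with T1 but no T2 score 0.5 SD worse at T1 than those kept, and that wait-list losses are random. The part of the bias that keeping their T1 scores would remove is about 0.05 × 0.5 = 0.025 SD. Those missing T1 itself are hardly helped, because only T0 informs their T1 value.

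**5. When bias arises at all.** A simulation of 4,000 trials used 60 per arm, three visits with correlation 0.5, no true effect, and about 15% lost after T1. The correlation and dropout patterns are assumptions. The completer analysis compared the mean of T1 and T2 between arms, adjusted for T0, among those with all visits. The comparator was a likelihood-type estimate of the same quantity that keeps every T1 score. Negative values favour LiON.

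| Assumed dropout | Completer bias (SD) | Completer type I error | Likelihood bias (SD) |
|---|---|---|---|
| Random in both arms | 0.00 | 4.9% | 0.00 |
| More distressed leave, both arms | 0.00 | 5.1% | 0.00 |
| About 25% of LiON (more distressed), random 5% of wait-list | −0.15 | 17.8% | 0.00 |
| More distressed leave LiON, improved leave wait-list | −0.20 | 31.7% | 0.00 |

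Under random dropout the completer estimate varied 1.05 times as much as the likelihood estimate, so the loss of precision alone is small. In every row dropout depends on T1, which is observed. Missing at random therefore holds by construction, and all losses fall after T1. This is the setting most favourable to a mixed model.

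**The case against.** The strongest objection is that much of this rests on what the Protocol does not say. It names neither GLM nor a complete-case rule. Imputation before the ANCOVA, or a fit through SPSS MIXED, would be compatible with its wording. Analysis sets and missing-data rules often sit in a statistical analysis plan, and none is among the documents reviewed. If only T0 and T1 are modelled, nobody is lost for missing T2. All of that stands, and it is why the point is conditional. It does not remove the point, because section 7 does fix a named method whose usual implementation deletes incomplete cases, and section 3.2.1 makes the three-visit model the natural reading.

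A reader might infer that the primary analysis simply becomes a completer analysis. The text does not support that: no passage limits the analysis to completers, and section 7 does not label the model primary, although it is the only one named. Nor does raising the target for attrition show it, since that is routine whatever the analysis set.

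A reader might also take the whole 15% as lost from LiON, at an assumed 0.5 SD worse, and set 0.15 × 0.5 = 0.075 SD against the planning effect. That overreaches in two ways. It counts people missing T1, whom the better model barely recovers. It also treats the planning effect as a standardised mean difference, whereas section 6 says only that "LiON yields an effect size of 0.4 when compared with controls with no intervention at all" and that "we estimate the effect size could be halved", without giving the metric.

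Finally, arm-differential dropout is conjecture. No passage reports it, and the larger biases in the simulation come only from asymmetric patterns that were assumed.

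**Conclusion.** The point holds in conditional form. Run as conventional repeated-measures ANCOVA on T0, T1 and T2, with no separate handling of missing data, the named analysis could exclude up to about 18 of 120 randomised participants. That leaves 102 against the 104 planned, and between 0 and 18 of those excluded would have an observed T1 score.

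Bias is about zero if dropout is random or similar in both arms. In two assumed asymmetric patterns it reached −0.15 and −0.20 SD, with type I error of 17.8% and 31.7%. Those figures show what could happen and are not a forecast for this trial. For the T1 contrast under the 10%/15% split, the recoverable bias is about 0.025 SD.

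The conclusion rests on the GLM form, on all three visits being in the model, and on the assumed correlation and dropout patterns. The change is worth making because it costs little and removes an avoidable exposure.

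**What to change.** In section 7, replace the repeated-measures ANCOVA with a linear mixed model fitted by the SPSS MIXED procedure. State that:

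- all randomised participants are included in the arm to which they were assigned;
- every observed T1 and T2 score is used, with no deletion for a gap at another visit;
- visit is categorical and the within-participant covariance is unstructured;
- baseline distress is adjusted for, either as a covariate or as a response with equal arm means at T0;
- the group difference at T1 is the LiON-versus-control contrast.

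The text should add that this model removes bias only if data are missing at random. A sensitivity analysis that shifts imputed LiON values by a range of amounts would probe that assumption, but it is optional.

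The cost is a rewording of section 7 and slightly more analysis work. Software, data collection and visit schedule stay the same.

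### The look at 60 subjects may reset sample size and allocation with no named error control; if it compares the arms, an ordinary final test at 0.05 can exceed 5%

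*Protocol*

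**What the plan says.** Protocol Section 7 (Statistical Analysis) states: "A planned analysis will take place after data is available for the first 60 subjects". Its purpose is a better estimate of power, which is then used "to adjust the final sample size and allocation to the study arms, according to the principles of adaptive trial design". The same section says: "All statistical analyses will be carried out using IBM® SPSS® with the significance level set at 0.05". It names a repeated-measures ANCOVA of change in distress between the two groups. It names no combination test, adjusted level or term for recruitment stage.

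Section 4.1 gives the starting design: "This study will adopt an open labelled wait list RCT design", with 60 in the LiON group and a "wait list control (WLC) group (n = 60) in a 1:1 ratio".

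Section 6 supplies the planning values. The pilot is reported as "LiON yields an effect size of 0.4 when compared with controls with no intervention at all", and then "we estimate the effect size could be halved, with alpha = 0.05 and power = 80%, 52 subjects are needed for each group". The effect is given only in standardised form, with no difference in scale points, no SD and no correlation between visits.

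**The concern.** Two separate problems arise if the look compares the arms.

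- **Error rate.** When the second-stage size or ratio is chosen from the first-stage difference, the weight given to each stage depends on the first-stage result. An ordinary pooled test ignores this, so a p-value below 0.05 need not carry a 5% error rate. Error control cannot reliably be restored after an unplanned, data-driven change, so the method has to be settled before the look.
- **Calendar time.** If the ratio changes after 60 subjects, one arm holds more late recruits than the other. Section 2.1 describes successive COVID-19 waves and tightening restrictions, so mean distress may move between the two stages. A pooled comparison with no stage term would attribute part of that movement to treatment.

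The look is also likely to prompt a change. The stated 52 per group does not follow from the halved effect on the usual two-group calculation, so an interim power check could well suggest a very different N.

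**Working it through.** **Inputs.** Level 0.05 (Sections 6 and 7; taken as two-sided, since sidedness is not stated), power 80%, effect 0.4 halved to 0.2 (Section 6; read as a standardised mean difference, since the metric is not stated), 60 per arm at 1:1 (Section 4.1), look at 60 subjects, so 30 per arm (Section 7). The re-estimation rule, caps, new ratio and calendar shift are not in the protocol and are assumed below, with ranges.

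**1. The plan's own figure.** n per group = 2(1.96 + 0.84)² / d², where the squared sum is 7.849 before rounding.
- d = 0.2: 2 × 7.849 / 0.04 = 392.4, so 393 per group. At 52 per group the power is about 17%.
- d = 0.4: 2 × 7.849 / 0.16 = 98.1, so 99 per group.
- The stated 52 is not reproduced by this calculation. It appears only under choices that the protocol does not state, such as a paired t-test at 0.4.
- Attrition: 104 × 1.15 = 119.6, which gives the stated 120.

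**2. Precision at the look.** The SE of the standardised difference with 30 per arm is √(2/30) = 0.258. If the truth is 0.2, a result one SE high is 0.458 and suggests 2 × 7.849 / 0.458² = 74.8, so 75 per arm. A result one SE low is −0.058, which has the wrong sign.

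**3. Type I error when N follows the observed effect.** Under no effect, draw independent stage statistics z₁ and z₂, with n₁ = 30 per arm. Set d̂ = |z₁|√(2/30). Re-set N per arm to 2 × 7.849 / d̂², held between a floor and a cap, with n₂ = N − 30. The ordinary final test is (√n₁ z₁ + √n₂ z₂)/√N against ±1.96.

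| Total cap (assumed) | N never below 120 | N may fall to 60 |
|---|---|---|
| 180 | 0.056 | 0.064 |
| 240 | 0.060 | 0.068 |
| 480 | 0.066 | 0.074 |
| 1,200 | 0.070 | 0.078 |

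**4. Rules and tests that hold the level.**
- Blinded re-estimation of the variance with the ordinary test: 0.049.
- N increased only when conditional power is at least 50%, with the ordinary test: 0.048.
- Inverse-normal combination (z₁ + z₂)/√2, with equal weights fixed from the planned 60 + 60: 0.050 under the sample-size rules simulated.

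**5. Allocation alone, N kept at 120.** If the second-stage ratio were chosen from the first-stage result so as to maximise the error, it would reach 0.061 (one arm's share between 1/3 and 2/3) or 0.072 (share between 0.2 and 0.8). These are upper bounds, not forecasts.

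**6. Calendar period.** Suppose the last 60 are split 40:20. The arms then hold 70 and 50, with late shares 40/70 = 0.571 and 20/50 = 0.400. Crude bias = (0.571 − 0.400) × shift = 0.171 × shift.
- Shift 0.2 SD: bias 0.03 SD; pooled type I error 0.053.
- Shift 0.5 SD: bias 0.09 SD; 0.067.
- Shift 0.8 SD: bias 0.14 SD; 0.086.
- At 1:1 the late shares are equal and the bias is zero. With the analysis stratified by stage, type I error is 0.049 to 0.051.

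**The case against.** The strongest reply is that the protocol never says the look is by arm. Open label describes what participants know, not what the interim analyst computes, and a better estimate of power could come from pooled data. A reader might infer that the plan uses unblinded results and therefore inflates the error rate. The text supports neither step as fact: by-arm use is an inference, and inflation depends on a rule that is not given. Testing at 0.05 is not itself a fault, since a combination test is also run at 0.05. The reference to adaptive-design principles, or a statistical analysis plan not shown here, could supply the method. All of this stands, and it makes the conclusion conditional.

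It does not remove the point. Section 6 powers the trial on a standardised effect alone, so a pooled SD could not update power as the plan is written. An outcome-driven reason to change allocation also needs by-arm results.

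Three further readings go too far:
- **A worst case near 11%.** This needs a second-stage size picked to maximise the error, which nobody proposes.
- **A bias of 43% of the planned effect** (0.086/0.2). This is a crude bias in outcome level under an assumed 2:1 ratio and 0.5 SD shift. Section 7 analyses change, so a shift present at both baseline and post-intervention would cancel. With baseline adjustment at an assumed slope of 0.5, about half would remain.
- **A contradiction between Sections 4.1 and 7.** Section 4.1 gives the starting ratio and Section 7 announces in advance that it may be adapted, so the two can stand together.

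**Conclusion.** The point holds conditionally. Section 7 commits to changing both N and allocation midway, at an unadjusted 0.05, without saying whether the arms will be compared or how the error rate would be protected if they are.

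If N is re-set from the observed difference and an ordinary test follows, the true level is about 5.6% to 7%, or 6.4% to 8% if N may also fall. The excess is modest but avoidable. These figures rest on a two-sided test, 30 per arm at the look, re-powering to 80% at the observed effect, and the assumed caps. A blinded or promising-zone rule would leave the level near 5%.

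The calendar effect arises only if the ratio changes and the stages are pooled. Its crude size of 0.03 to 0.14 SD rests on an assumed 2:1 second stage and an assumed shift, and it overstates what would remain in an analysis of change.

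**What to change.** Rewrite the interim paragraph of Section 7 before the look takes place.

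1. **Allocation.** Keep 1:1 throughout. If it must change, stratify the final analysis by stage; if by-arm results drive the change, use the combination test in item 3 as well.
2. **Preferred: a non-comparative look.** At 60 subjects, use only the pooled SD, the pooled correlation between visits and overall attrition, and compute no group comparison. This requires a raw target difference on the distress scale, stated beforehand, because a standardised target does not respond to a new SD. Section 6 therefore has to be revised at the same time, including the basis for 52 per group.
3. **If by-arm results are to change N.** Fix the rule and the maximum N before the look, always recruit a second stage, and test at the end with an inverse-normal combination using weights pre-set from the planned 60 + 60 split.

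The text change is short, but setting the raw target and revisiting Section 6 is real work. The price is that N can no longer be steered freely by the observed effect. Little is lost, since 30 per arm estimates that effect with an SE of about 0.26 SD.
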